14.5 Procedures for Reporting Deviation(s) from the Original SAP

These will be submitted as substantial amendments where applicable and recorded in subsequent versions of the protocol and SAP.

14.6 Termination of the Trial

Progression criteria for the internal pilot phase are described in Section 9.12. There is the potential for the trial to terminate early if our funder assesses the trial as not being feasible following assessment of progress against our targets at the end of the internal pilot with input from our TSC and IDMC.

14.7 Inclusion in Analysis

All randomised participants will be included in the primary intention-to-treat analysis. As part of sensitivity analyses, ineligible/unevaluable participants will be excluded from the analysis population.

15 Analysis

15.1 Main Analysis

For the statistical analysis of the primary outcome (proportion of 'successes' and 'failures' of pain control in the first 5 postoperative days for each participant, as defined in Section 14.3), we will use the intention-to-treat population and fit a multilevel logistic regression model, with the minimisation variables and condition (PAD or diabetes) as fixed-effect covariates and with random centre effects, to test for a difference between treatment arms at a 5% two-sided alpha level. Secondary outcomes will be analysed using similar multilevel regression models depending on the type of outcome (see Table 8) with the same covariate adjustments using the intention-to-treat principle. We will account for possible 'truncation by death' in sensitivity analyses. Additional secondary analyses considering the level of intervention fidelity will also be undertaken, including successful placement of the PNC, the PNC remaining in place for 5 days, and the local anaesthetic being infused within the dose and

rate ranges specified in the protocol for 5 days. All treatment effects will be reported as point estimates with 95% confidence intervals and p-values.

Table 8 Summary of Analysis for Secondary Outcomes

Outcome	Measure	Time frame	Analysis
Average pain	NRS	5d	Linear regression of median or mean (adjusted for baseline)
Overall satisfaction with analgesia	Likert scale	5d	Linear regression of transformed measure (if appropriate)
Total opioid use	Morphine equivalents	5d	Linear regression (adjusted for baseline)
Opioid side effects	Frequency and severity of symptoms	5d	Linear regression of transformed measure (if appropriate)
Surgical site infection	Proportion of people with infection	30d	Logistic regression
Delayed wound healing	Proportion of people with delay	30d, 6m	Logistic regression
Residual limb surgery	Proportion of people with surgery	30d, 6m	Logistic regression
Phantom limb pain	NRS	3m, 6m	Linear regression
Chronic stump pain	NRS	3m, 6m	Linear regression
Health utility/QoL	EQ-5D-5L	3m, 6m	Linear regression of transformed measure (adjusted for baseline)
Depression	HADS	3m, 6m	Linear regression of transformed measure (adjusted for baseline)
Prosthesis fitting	Proportion of people using prosthesis Time to achieve fitting	3m, 6m	Logistic regression Cox regression

Level of independence	SIGAM grading	3m, 6m	(Ordered) logistic regression, tabulation
independence			
Mortality	Proportion of people dead	6m	Logistic regression
	Time to death		Cox regression
	Cause of death		Tabulation
Hospital stay	Time to discharge	6m	Cox regression
Hospital re-	Proportion of people re-	6m	Logistic regression
admissions	admitted		
DOAH-90	Days alive and out of	90d	Linear regression of transformed
	hospital		measure (if appropriate)
Postoperative	Clavien-Dindo grading	At	(Ordered) logistic regression,
complications		discharge	tabulation
MLLA of	Proportion of people who	6m	Logistic regression
contralateral limb	were a unilateral amputee		
	who subsequently		
	underwent contralateral MLLA.		

A comprehensive SAP will be finalised prior to database lock by the trial statistician, with support from the TMG, and agreed by the TSC.

15.1.1Sub-group and Interim Analysis

No interim analysis is planned. Sub-group analyses may be performed for sex, history of diabetes mellitus, anaesthetic given, type of infusion device used and level of amputation. Any planned sub-group analyses will be agreed by the TMG and pre-specified in the SAP.

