5.1 Primary Objectives

Our primary objective is to compare 'freedom from pain' in participants undergoing MLLA randomised to receive PNC placement, with participants undergoing MLLA who are randomised not to receive PNC placement, defined as the proportion of time points with self-reported pain ≤3 on a 0-10 NRS, assessed twice daily for the first five postoperative days.

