5.3 Primary Outcome Measure

Our primary outcome will be 'freedom from pain' defined as the proportion of time points with selfreported pain \leq 3 on a 0-10 NRS, assessed twice daily (am and pm, separated by > 4 hours) for the first five postoperative days.

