14.1 Randomisation

Participants will be allocated via covariate minimisation on the planned level of amputation (BKA vs. TKA vs. AKA), type of anaesthesia (general vs. neuraxial), preoperative pain score, and recruitment site. Allocation will be in a 1:1 ratio to either active treatment (placement of a PNC with a postoperative infusion of local anaesthetic in addition to standard anaesthetic and postoperative analgesia) or control (standard anaesthetic and postoperative analgesia alone). A random element will be added to the (otherwise strictly deterministic) minimisation algorithm to reduce predictability [REF: www.bmj.com/content/330/7495/843].

Computerised web-based remote randomisation (available 24 hours a day) will be used. A 9am-5pm telephone back up will be available for use if the online system does not work or the site has problems accessing the online website. A detailed randomisation plan will be finalised and signed off prior to any participant being randomised.

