14.3 Sample size

'Good' pain control is defined as \leq 3 on a 0-10 NRS (66). Feasibility trial participants in the control arm reported 'freedom from pain' (defined as NRS \leq 3, or pain \leq 'mild' on a 4-point Verbal Rating Scale) 61.7% of the time in the first 5 postoperative days. Treatment arm participants reported 'freedom from pain' 76.8% of the time, a relative improvement of 24.5%. Using a more conservative (but still clinically important) relative improvement of 20% between arms results in a sample size of 299 participants per arm for 90% power when using a two-sample test for proportions with two-sided 5% alpha. In our feasibility trial, 45 of the 49 participants (92%) provided primary outcome data (defined as a participant providing outcome data for pain in >50% of possible timepoints). To account for this, a sample size of 650 is required.

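### The primary logistic model names centre as its only random effect, so as written it treats one participant's repeated pain readings as independent and the 5% test is anti-conservative

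*Protocol*

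**What the plan says.** Protocol section 5.1 has pain "assessed twice daily for the first five postoperative days", which gives up to 2 × 5 = 10 binary readings per person (score of 3 or less, or not). Section 5.3 repeats the twice-daily schedule. Section 15.1 defines the response as the "proportion of 'successes' and 'failures' of pain control in the first 5 postoperative days for each participant". It then says the analysts will "fit a multilevel logistic regression model, with the minimisation variables and condition (PAD or diabetes) as fixed-effect covariates and with random centre effects". The arms are compared in this model by a two-sided test at the 5% level.

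Section 14.1 lists the minimisation variables as planned amputation level, "type of anaesthesia (general vs. neuraxial), preoperative pain score, and recruitment site". Section 15.1 carries the same covariate adjustment over to the secondary outcomes.

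Section 14.3 sizes the trial with a two-sample test for proportions. It counts someone as contributing primary outcome data if they are "a participant providing outcome data for pain in >50% of possible timepoints", that is, at least 6 of 10 readings. Section 14.4 expressly leaves missing-data detail to the SAP. Section 15.1 says that a full SAP will follow, but it does not mark the random-effects structure as still to be decided.

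**The concern.** A binomial or logistic likelihood with a centre effect alone assumes that, given centre and covariates, the readings from one person are independent trials. Repeated pain scores in one patient over five days can be expected to be positively correlated, because some patients have well-controlled pain throughout and others do not. Treatment is allocated per participant, so this correlation bears directly on the treatment contrast. A centre effect does not absorb it.

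What is at stake is the trial's single confirmatory test: confidence intervals that are too narrow, and a false-positive rate above the stated 5%.

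The same sentence has a second, smaller problem. Site is a minimisation variable, so a literal reading enters it as a fixed effect and again as a random centre effect.

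**Working it through.** **1. The plan's own sample size.** Inputs from section 14.3: control rate "61.7% of the time in the first 5 postoperative days", relative improvement 20%, two-sided 5%, 90% power. The treatment rate is 0.617 × 1.20 = 0.7404, the difference is 0.1234 and the mean rate is 0.6787. With the pooled two-proportion formula:

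n = [1.960 × √(2 × 0.6787 × 0.3213) + 1.282 × √(0.617 × 0.383 + 0.7404 × 0.2596)]² / 0.1234² ≈ 299 per arm.

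The total is 598 / 0.92 = 650. Both figures reproduce. The calculation gives each participant one yes/no result, which is the ICC = 1 case.

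**2. Type I error of the model as written.** With m readings per participant and a common within-participant correlation, the design effect is DE = 1 + (m − 1) × ICC. The model's standard error is too small by a factor √DE, so

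true error = 2 × [1 − Φ(1.96 / √DE)].

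Example with m = 10 and ICC = 0.2: DE = 2.8, √DE = 1.67, 1.96 / 1.67 = 1.17, error = 24%.

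The protocol gives no ICC, so the values below are assumptions. The relevant ICC is the residual one, after adjustment for the model's covariates.

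**3. Simulation under no treatment effect.** 598 participants, 14 centres, beta-binomial readings with mean about 0.617, 2,000 runs per setting. Centre was adjusted for with fixed effects as a stand-in for random centre effects.

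| Assumed ICC | Formula, 10 readings | Formula, 6 readings | Simulated, 10 readings | Simulated, 6–10 readings |
|---|---|---|---|---|
| 0.05 | 10.4% | 8.0% | 9.8% | 10.3% |
| 0.1 | 15.5% | 11.0% | 15.7% | 12.4% |
| 0.2 | 24.1% | 16.6% | 25.0% | 22.4% |
| 0.3 | 30.8% | 21.5% | 31.2% | 26.4% |
| 0.4 | 36.1% | 25.8% | 36.9% | 31.8% |
| 0.5 | 40.3% | 29.5% | 41.2% | 38.0% |
| 0.6 | 43.8% | 32.7% | 47.2% | 39.8% |

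At ICC 0.05 the two simulated columns differ by no more than simulation error.

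**4. Decaying correlation.** If correlation falls with time between readings (first-order autoregressive, 10 readings), DE = 1 + 2 Σ (1 − k/10) ρᵏ for k = 1 to 9. The error is 14% at lag-1 correlation 0.3, 22% at 0.5, 34% at 0.7 and 40% at 0.8.

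**5. The same model with clustering handled.** With participant-level robust standard errors on the same simulated data, rejection was 4.3% to 6.5% over all settings, including a near-zero ICC of 0.001. The Monte Carlo standard error at 5% is √(0.05 × 0.95 / 2000) ≈ 0.5 percentage points.

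**6. Effect of the correction on power.** With 299 per arm and 10 readings, the effective number of readings per arm is 299 × 10 / (1 + 9 × ICC). Power is 90.0% at ICC 1 (299 effective readings), 98.2% at 0.6 (467) and 99.2% at 0.5 (544).

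**The case against.** The best defence is that the sentence leaves room. The word multilevel does not exclude a participant level. The response is described per participant, which could mean a fractional or quasi-binomial model of one proportion per person. Only a plain binomial model with centre effects produces the inflation. The SAP, which is not shown, may settle this. One outcome per person in the sample size also suggests that the planners think of the participant as the unit.

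This limits the claim but does not remove it. Section 15.1 goes beyond naming a model family: it lists the effects, and centre is the only random one. No participant-clustered method is named for the primary analysis anywhere in the protocol. An analyst who follows the text literally would run an invalid test.

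The defence is right about magnitude. A reader might infer that the test would reject a true null 25–40% of the time. The documents do not support that as a flat figure. With 10 complete readings it needs an ICC of about 0.21 to 0.49. With 6 readings it needs about 0.38 to 0.88. Adjustment for preoperative pain, amputation level and anaesthesia should also lower the residual correlation.

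Two other inferences fail. The contrast with section 14.3 does not show the trial to be wrongly sized, because one result per person is the conservative extreme. And entering site twice is not shown to damage the primary test: the random-effect variance would fall to about zero, leaving essentially a fixed-site model. In the secondary logistic models, with about 14 sites, it would mean about 13 site terms. The documents give no event rates from which to judge the harm.

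**Conclusion.** The point holds as an error in the model as written. It does not establish what the final analysis will do, since a participant term could still be added under the existing wording or in the SAP. If none is added, the two-sided 5% test is anti-conservative for any positive residual within-participant correlation. Over assumed ICCs of 0.05 to 0.6 with 10 readings, the formula gives a type I error of about 10% to 44%. Even the lowest of these is about double the nominal level. These figures rest on an assumed ICC and, apart from step 4, on equal correlation between all pairs of readings. The duplicate entry of site is a genuine but secondary wording conflict. Because the confirmatory test is affected and the correction is cheap, it should be made before any analysis.

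**What to change.** In section 15.1, state that the primary model has readings nested in participants nested in centres, with a participant random intercept and a centre random intercept.

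Alternatively, choose and name one participant-clustered method:

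- a beta-binomial or quasi-binomial model of each participant's count, with centre effects; or
- GEE with robust standard errors at participant level and centre adjusted for.

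These are not interchangeable. A participant random intercept gives an odds ratio conditional on the participant, whereas GEE gives a marginal one. The text should say which is the target.

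Enter recruitment site once only, as the random centre effect, in the primary model and in the secondary models that inherit its covariates. The remaining minimisation variables stay as fixed effects.

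The cost is protocol and SAP wording. No new data and no more participants are needed, and 299 per arm (650 in total) can stand.

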Immediate postoperative pain management commonly involves epidural or intravenous (IV) patientcontrolled analgesia, which relies on opioid based agents. A recent UK wide National Confidential Enquiry into Patient outcome and Deaths review into lower limb amputations found that strong opioids were the most frequently used type of postoperative analgesia (22). While opioids provide excellent pain relief, they also have many associated side effects, including nausea and vomiting (23), constipation (24), sedation and pruritus (25). Morphine is normally self-administered via a pump, and

Trials Research Canolfan Ymchwil Treialon

Centre for

therefore the patient experiences pain before self-treating. Tolerance, dependence, and addiction to opioids can occur with prolonged use (26,27). The pharmacokinetics of opioids are altered with increasing age, deteriorating renal function and polypharmacy, all of which are common in people with PAD and/or diabetes, leading to unpredictable adverse drug effects and interactions (28). Furthermore, opioid related side effects are problematic, increasing in-hospital costs by 7 to16% and overall length of stay by approximately 10% (29,30). Acute postoperative opioid use costs £23/day/patient (31).

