12.1 Assessments

12.1.1 Baseline

The baseline assessment consists of collecting the following information:

- Preoperative pain assessed by the NRS
- Participant satisfaction of pain management during the preceding 24 h, assessed using a 4point Likert scale
- Preoperative opioid and analgesic use
- Health-Related QoL assessed using EQ-5D-5L (59)
- Depression measured by the Hospital Anxiety and Depression Scale (HADS) (60)
- Past surgical and medical history, including cigarette use and type of diabetes mellitus
- Health services contact
- Results from the routinely collected pre-operative blood tests, including liver and renal function tests
- Planned level of amputation
- Body weight
- Residential status on admission
- Review of pre-operative resting 12-lead ECG
- (For participants of child-bearing potential) Review of pre-operative pregnancy test result

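### Age is adjusted for in no analysis and preoperative opioid use in only one, although both are known before randomisation; adding them would be a cheap gain in efficiency

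*Protocol*

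**What the plan says.** Section 15.1 specifies a multilevel logistic model for the primary outcome. Its fixed effects are the minimisation variables and condition, and centre effects are random. Section 14.1 lists the minimisation variables: planned amputation level, type of anaesthesia, preoperative pain score and recruitment site.

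Secondary outcomes follow models chosen by outcome type in Table 8, "with the same covariate adjustments using the intention-to-treat principle". Table 8 then adds a baseline adjustment in four rows: average pain, total opioid use, EQ-5D-5L and HADS. For total opioid use, the natural reading of that baseline is preoperative opioid use. The other rows carry no added term.

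Section 12.1.1 lists "Preoperative opioid and analgesic use" among the baseline items, and Table 2 takes it from the medical notes. Age is not named in the Section 12.1.1 list, but it must be known to confirm eligibility (Section 8.1) and is implied by the demographics row of Table 2.

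Section 4.1 says that opioid pharmacokinetics change with "increasing age, deteriorating renal function and polypharmacy, all of which are common in people" with PAD and/or diabetes, and that tolerance can develop with prolonged opioid use. Section 11.4 makes the local anaesthetic ceiling depend partly on age.

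**The concern.** The protocol does not leave the covariates open. It states a set for the primary outcome and carries it to the secondary outcomes. That set is built around acute pain, and it omits two variables that the protocol's own background treats as relevant to analgesic response.

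- **Primary outcome.** Preoperative pain score is included. However, the same score can mean different things in a patient on long-term opioids and in one on none, and the score alone cannot separate them.
- **Secondary outcomes without a baseline term.** Mortality, DAOH-90, time to discharge, prosthesis fitting and SIGAM grade rely on the common set alone. Age is an obvious candidate predictor for all of them.

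Because neither variable is a minimisation factor, the design does not balance them beyond what chance provides, and the written models do not correct a chance imbalance. What is at stake is a modest amount of power, not validity.

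**Working it through.** **1. Where each variable enters, as written**

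| Analysis | Age | Preoperative opioid use |
|---|---|---|
| Primary outcome | no | no |
| Total opioid use | no | yes, as the baseline value |
| Average pain, EQ-5D-5L, HADS | no | no (own baseline only) |
| All other Table 8 rows | no | no |

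**2. The protocol's own sample size (Section 14.3)**

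Inputs:
- control proportion: "61.7% of the time in the first 5 postoperative days"
- effect: "relative improvement of 20% between arms", so p2 = 0.617 × 1.2 = 0.7404
- method: "two-sample test for proportions with two-sided 5% alpha"
- result claimed: "299 participants per arm for 90% power"
- data provision: "45 of the 49 participants (92%) provided primary outcome data"

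With the pooled formula, the mean proportion is p̄ = (0.617 + 0.7404)/2 = 0.6787 and the difference is 0.1234:

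n = [1.960 × √(2 × 0.6787 × 0.3213) + 1.282 × √(0.617 × 0.383 + 0.7404 × 0.2596)]² / 0.1234² = 299 per arm after rounding up.

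Power at 299 per arm is 90.0%. The total is 598/0.92 = 650. The stated figures reproduce, and they assume no covariate adjustment.

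**3. What adjustment could add**

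The protocol gives no correlation between these variables and the outcome. **Assumption:** after the planned covariates, age and preoperative opioid use together have partial correlation r = 0.10 to 0.30 with a participant's freedom-from-pain proportion. On a linear scale the effective sample is 598/(1 − r²). Power is the formula of step 2 evaluated at 299/(1 − r²) per arm.

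| r | Effective sample | Gain on 598 | Power |
|---|---|---|---|
| 0 | 598 | 0 | 90.0% |
| 0.10 | 598/0.99 = 604 | 6 | 90.3% |
| 0.20 | 598/0.96 = 623 | 25 | 91.1% |
| 0.30 | 598/0.91 = 657 | 59 | 92.5% |

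The base is 598 because the other 52 of the 650 are allowed for as providing no primary outcome data.

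**4. How far the approximation reaches**

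The formula belongs to linear models. In the primary logistic model, and in the other logistic and Cox models, adding a prognostic covariate generally does not shrink the standard error of the log odds ratio or log hazard ratio. The gain comes as power, because the conditional effect lies further from the null. The 90.0% starting point is the power of an unadjusted two-proportion test, not of the planned model, so the table shows the order of the gain only.

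**5. Sensitivity to missing baseline data**

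If a fraction m of analysed participants were dropped for a missing covariate, the effective sample would be 598(1 − m)/(1 − r²). This returns to 598 when m = r². At r = 0.10 the gain is lost at 1% missing, and at r = 0.30 at 9% missing. The gain therefore depends on not dropping anyone.

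**The case against.** The strongest case against is that this is a preference. Adjusting for the minimisation variables and one disease factor is a valid pre-specified choice that matches the allocation method. It already includes the preoperative pain score, which is the baseline of the primary construct. Section 15.1 also promises a comprehensive SAP, where further covariates could be named. This stands as far as validity goes. It does not remove the point, because Section 15.1 states a set that omits both variables.

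Two stronger readings are tempting, and the document supports neither.

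- A reader might infer that a single covariate set is imposed on every outcome. Table 8 adds a baseline term in four rows, and in one of them that term is preoperative opioid use.
- A reader might infer that precision is being lost across all comparisons. In the logistic and Cox rows the standard error would generally not fall, and the size of any gain rests on an assumed correlation.

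It is also fair to say that Sections 4.1 and 11.4 concern pharmacokinetics, tolerance and dose safety. They make the two variables plausible predictors, but they do not show that either predicts pain control once preoperative pain is adjusted for.

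Finally, the primary analysis is complete-case (Section 14.4), and preoperative opioid use is taken from medical notes. The protocol states conversion to morphine equivalents only for postoperative use. Step 5 shows that this matters, but simple imputation of the baseline value removes the problem.

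**Conclusion.** The point holds as a low-cost efficiency improvement. Age is adjusted for in no analysis, and preoperative opioid use only in the total opioid use analysis, although both are available before randomisation. Nothing in the planned analysis is invalid or biased, and the sample size of 299 per arm and 650 in total stands.

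Under the assumed partial correlation of 0.10 to 0.30, the benefit for the primary outcome is about 0.3 to 2.5 percentage points of power, or about 6 to 59 analysed participants. A weaker correlation would make it negligible. The argument for age is stronger for the secondary outcomes that have no baseline term, but no figure is offered there: the protocol gives neither a six-month mortality rate nor the strength of age as a predictor.

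**What to change.** In Section 15.1, or in the SAP before it is signed:

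- Add age (continuous) and preoperative opioid use as fixed covariates in the primary model. Code opioid use as none/some, or as daily morphine equivalents if the baseline doses are recorded reliably enough to convert.
- Add age to the secondary models that have enough events, with priority to mortality, DAOH-90, time to discharge, prosthesis fitting and SIGAM grade.
- State that missing baseline covariate values will be filled by simple imputation that ignores treatment arm, so that no participant leaves the complete-case analysis for this reason.

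The cost is one line of text, one or two more parameters per model, and a rule for missing baseline values. No new data collection is needed. Because the trial is open-label, naming the covariates early also avoids any appearance that they were chosen after seeing the data.

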5.4 Secondary Outcomes measures

Secondary outcome measures:

(First 5 postoperative days)

- Participant satisfaction related to pain management during the preceding 24 h, assessed preoperatively and once daily postoperatively for up to five days using a 4-point Likert scale
- Opioid use assessed once daily postoperatively for five days, converted to morphine equivalents using the University of Alberta Multidisciplinary Pain Centre Opioid Conversion Guide (54)
- Opioid side effects (frequency and severity of symptoms) assessed once daily postoperatively for five days

(At discharge)

- Morbidity, assessed using Clavien-Dindo grading at discharge
- Length of hospital stay

(At 30 days)

Surgical site infection rates classified as per the 2008 CDC/NHSN document assessed at 30 days (55)

(At 90 days)

• Days alive and out of hospital assessed at 90 days (DAOH-90)

(At 3 to 6 months)

- Chronic residual limb pain assessed at 3 and 6 months
- Phantom limb pain assessed at 3 and 6 months
- Length of hospital stay assessed at 3 and 6 months
- Residual limb surgery assessed at 30 days, 3 months, and 6 months
- Health-related QoL assessed using EQ-5D-5L at 3 months and 6 months
- Participant reported anxiety and depression assessed using HADS at 3 months and 6 months
- Prosthesis fitting assessed as rate and time to fitting using SIGAM at 3 and 6 months
- Assessment of health care resource usage during the first 6 months postoperatively
- Mortality assessed at 6 months.

6 Trial Design and Setting

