14	Randomisation	CRF	-			X						Once	Site Research team
15	Method of anaesthesia	Medical notes and CRF	Surgery CRF			X						Once	Site Research team
16	Pre-operative regional nerve block performed, and drugs used	Medical notes and CRF	Surgery CRF			X						Once	Site Research team
17	Intraoperative nerve management	CRF, documente d in surgical notes	Surgery CRF- Successful identificati on of nerve, method			X						Once	Site Research team

Data	а Туре	Source Data	Data type	Screening	Baseline/ Pre- operative assessment	At Operation	First 5 Post- operative days	30 days	At discharge	3 Month FU	6 Month FU	Freque ncy	By whom
			used to cut nerve and whether it was tied.										
18	Actual level of amputation	Medical notes and CRF	Surgery CRF			X						Once	Site Research team
19	Postoperative pain	CRF	11-point NRS				X					Twice daily	Partcipant reported
20	Overall satisfaction with analgesia	CRF	5-point scale (0 to 4)		X		x					Once daily	Participant reported
21	Total opioid use (converted to morphine equivalents)	Medical notes					Х					Daily	Site Research team

Data	а Туре	Source Data	Data type	Screening	Baseline/ Pre- operative assessment	At Operation	First 5 Post- operative days	30 days	At discharge	3 Month FU	6 Month FU	Freque ncy	By whom
22	Opioid side effects	CRF	Frequency & severity of symptoms				x					Daily	Participant reported
23	(Intervention arm only) Fidelity of nerve catheter usage, specifically duration it remains in place, and duration of delivery of local anaesthetic	CRF	Catheter monitoring CRF				X					Daily	Site Research team
24	Surgical site infection	Medical Notes						X				Once	Site Research team

Data	а Туре	Source Data	Data type	Screening	Baseline/ Pre- operative assessment	At Operation	First 5 Post- operative days	30 days	At discharge	3 Month FU	6 Month FU	Freque ncy	By whom
25	Delayed wound healing	Medical Notes						X			x	Once	Site Research team
26	Residual limb surgery	Medical Notes						X			x	Once	Site Research team
27	Residential status upon discharge	CRF	Discharge form						x			Once	Site Research team
28	Resource use: Additional equipment and home adaptions	CRF	Discharge form						X			Once	Site Research team
29	Inpatient analgesic use	Medical notes							X			Once	Site Research team
30	Postoperative complications	Medical notes/ CRF	Clavien- Dindo grading						X			Once	Site Research team

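### Table 8 gives satisfaction with pain management no baseline adjustment, although it is measured preoperatively and the four other Table 8 outcomes with a baseline measure are adjusted for it

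*Protocol*

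**What the plan says.** **Measurement.** Section 5.4 of the protocol has satisfaction "assessed preoperatively and once daily postoperatively for up to five days using a 4-point Likert scale". The baseline list in 12.1.1 includes "Participant satisfaction of pain management during the preceding 24 h". Table 2 (row 20) marks it both at baseline and on the first five postoperative days.

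**Analysis.** The Table 8 row for overall satisfaction with analgesia reads "Linear regression of transformed measure (if appropriate"). Other rows name a baseline term: average pain has "Linear regression of median or mean (adjusted for baseline") and total opioid use has "Linear regression (adjusted for baseline"). The EQ-5D-5L and HADS rows specify a transformed measure together with baseline adjustment.

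**Common covariates.** Section 15.1 analyses secondary outcomes "with the same covariate adjustments using the intention-to-treat principle" as the primary outcome. These are the minimisation variables, the condition (PAD or diabetes) and random centre effects. By 14.1 the minimisation variables are planned amputation level, type of anaesthesia, preoperative pain score and site.

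**Scale.** Sections 5.2, 5.4, 12.1.1 and 12.1.3 describe a 4-point Likert scale. The Synopsis gives a 0 to 4 rating and Table 2 a "5-point scale (0 to 4").

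**The concern.** Table 8 decides baseline adjustment row by row, and satisfaction is the only one of its outcomes with a baseline measure that does not receive it. No reason is given. A statistician following the table would leave the preoperative score out of the comparison for which it was most plausibly collected.

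If that score predicts postoperative satisfaction beyond what preoperative pain already explains, leaving it out makes the residual variance larger than it need be. A chance difference between arms in prior satisfaction would also be corrected only so far as preoperative pain carries it, because minimisation balances pain and not satisfaction. The outcome matters to the trial: section 4.1 names satisfaction with care among the patient outcomes that good pain relief should serve.

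**Working it through.** **1. Rows side by side**

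| Table 8 outcome | Own baseline measure (12.1.1, Table 2) | Baseline adjustment in Table 8 |
|---|---|---|
| Average pain | yes | yes |
| Total opioid use | yes | yes |
| EQ-5D-5L | yes | yes |
| HADS | yes | yes |
| Satisfaction | yes | **no** |
| Opioid side effects, phantom pain, stump pain, SIGAM | no | no |

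The common covariates do not fill the gap, since preoperative satisfaction is neither a minimisation variable nor the condition covariate.

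**2. The plan's own figure.** The protocol states no power for satisfaction. Its sample size (14.3) reproduces. The control proportion is 0.617 and a 20% relative improvement gives 0.617 × 1.2 = 0.7404. With two-sided 5% alpha, 90% power, pooled variance and no continuity correction, the result is 299 per arm. Then 598 / 0.92 = 650. The sample size is not at issue. I use 299 per arm below as an assumed evaluable number for satisfaction.

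**3. Precision gained by adjusting.** Let r be the partial correlation between preoperative and postoperative satisfaction, given the covariates already in the model. Adding the baseline score multiplies the residual variance by (1 − r²), so

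power = Φ( d / √(2(1 − r²)/299) − 1.96 ).

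Here d is in residual SD units of the model without the baseline score. Setting power to 80% at r = 0 gives d = (1.96 + 0.842) × √(2/299) = 0.229. The last column is 299/(1 − r²) − 299.

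| r | 1 − r² | Power with adjustment | Equivalent extra participants per arm |
|---|---|---|---|
| 0.1 | 0.99 | 80.4% | 3 |
| 0.2 | 0.96 | 81.6% | 12 |
| 0.3 | 0.91 | 83.6% | 30 |
| 0.4 | 0.84 | 86.4% | 57 |
| 0.5 | 0.75 | 89.9% | 100 |

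Starting instead from 90% power (d = 0.265), the same values of r give 90.3%, 91.1%, 92.5%, 94.3% and 96.3%.

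**4. Which r is plausible.** Preoperative pain is already in the model, so the raw correlation overstates the benefit in the cases below. Let b be the raw correlation of baseline with postoperative satisfaction, a that of preoperative pain with the outcome, and c that of preoperative pain with baseline satisfaction, all taken as absolute values. Then

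r = (b − ac) / √((1 − a²)(1 − c²)).

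All three are assumptions. With a = 0.3 and c = 0.5, ac = 0.15 and the denominator is √(0.91 × 0.75) = 0.826:

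| b | r | Power |
|---|---|---|
| 0.2 | 0.06 | 80.1% |
| 0.3 | 0.18 | 81.3% |
| 0.4 | 0.30 | 83.6% |
| 0.5 | 0.42 | 87.1% |

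A gain of five points needs r of about 0.36, which in this example means b of about 0.15 + 0.36 × 0.826 = 0.45.

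**The case against.** The best reply is that this belongs to the SAP. Table 8 is only a summary, 15.1 promises a full SAP, the satisfaction row is itself left open, and nothing says that the preoperative score will not be used. The baseline label is also used loosely: for average pain it is redundant, because preoperative pain is already a covariate in every model.

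This stands in part. The SAP is not shown and may already include the term, so nobody should infer that the protocol forbids it. But the label is redundant only for pain. For opioid use, EQ-5D-5L and HADS it adds a covariate that the common set lacks, so its presence or absence has meaning. Section 15.1 requires the SAP only before database lock, in a trial that 14.2 says is not blinded, and a covariate added late could be questioned as data-driven.

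The second reply concerns size, and it stands. The preoperative item rates management of pain in a limb that is then removed, while the postoperative items rate analgesia after surgery. The correlation may be weak, and preoperative pain may carry part of it.

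A reader might also infer that the satisfaction comparison is biased. It is not: randomisation protects it without this covariate, and the confidence interval allows for chance imbalance.

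**Conclusion.** The inconsistency is real and sits in the protocol's own table. Its consequence is a loss of precision on one secondary outcome; neither validity nor the primary analysis or sample size is affected.

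It is tempting to say that the trial gives up a substantial amount of power, for example by taking a partial correlation of 0.5 as typical. The documents do not support that. They give no correlation, and even a raw correlation of 0.5 becomes 0.42 in the illustration above. What can be said is conditional. For an effect with 80% power without the term and an assumed 299 evaluable per arm, adjustment adds between about 0.4 points (r = 0.1) and 9.9 points (r = 0.5), and close to nothing below that range. The case for acting rests on consistency and negligible cost more than on a demonstrated gain.

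**What to change.** In the Table 8 satisfaction row, keep the linear regression and the option to transform, and add adjustment for baseline inside the existing bracket. Enter the preoperative satisfaction score as a covariate next to those in 15.1, and carry the same wording into the SAP. The transformation option should not be dropped, as it is the row's only provision for a short bounded score; the EQ-5D-5L and HADS rows already combine transformation with baseline adjustment.

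At the same time, reconcile the scale between sections 5.2, 5.4, 12.1.1 and 12.1.3 (four points) and the Synopsis and Table 2 (0 to 4), and confirm that baseline and follow-up use the same one.

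The cost is a short wording change, one degree of freedom and a simple rule for missing baseline scores. No new data are needed.
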